**Statistical Analysis:** *Power analysis and sample size calculation:* The sample size calculation was based on power estimates using our preliminary data on how acute postoperative pain contributes to PPP using the SAS "powerlog" macro. An updated analysis of our multi-center (three) chronic pain after total knee and hip arthroplasty survey study, evaluated one yr postoperatively, provided data for sample size calculation. The one yr follow-up data from this survey provides a conservatively estimate for the incidence of PPP at 6 mo, our primary outcome. To evaluate the effect of acute postoperative pain on incidence of PPP, our multi-center data was stratified based on chronic pain using our PPP criteria. Across the three centers, 259 TKR patients fell within criteria, of which 46 (17.8%) were identified with PPP at one year after surgery. Using a logistic regression, the acute postoperative NRS pain intensity was significant ( $P=0.0005$ ) with an odds ratio of 1.24 for each 1 point increase in acute postoperative NRS pain (95% Wald Confidence limits: 1.098-1.390). The average acute postoperative NRS pain for the entire sample was 5.5 (SD=2.9). Using the data to estimate predicted probability of PPP at the mean acute postoperative pain level, we have an incidence of 15.5% at the mean and 30.3% at the mean plus one standard deviation (NRS=8.4). A power analysis with 90% power and alpha of 0.05, using a logistic regression with no other covariates gives us a required sample size of 130. However, because we plan on utilizing multiple covariates, we estimate the multiple squared correlations at 0.5, raising our sample size estimated to 259. With a 15% dropout rate this values climbs to 298 (round to 300).

**Blinding of data:** To reduce bias, each co-investigator will only be involved in measurements specifically related to their specialization (Pain, Neurophysiologic, Psychosocial or Functional outcomes) and no others.

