**General statistical analysis:** Descriptive statistics will be reported as mean and standard deviation (SD) for continuous normally-distributed variables, and reported as counts and percentages for dichotomous variables. Assumptions will be evaluated and, if violated, either corrective measures will be taken (data-transformation) or other less restrictive methods will be implemented. Error inflation for multiple pre-planned comparisons will be corrected by using the Bonferroni step-down method. Models will be examined with no risk factors, with individual risk factors, and with multiple risk factors. The distribution of the primary outcome, NRS pain scores at 6 mo, will be evaluated, transformed to normal and then modeled as a continuous variable. If this is not possible, *then the dichotomous version*, as defined for PPP, will be used. We expect that the primary outcome of PPP (dichotomous) will be modeled using a logistic regression because the distribution of NRS pain scores from our preliminary survey data was strongly bi-modal (modes:0, 3). Thus it appears that this kind of distribution represents two distinct populations (a normally distributed pain population and a unimodal 'no-pain' population). Pain intensity (continuous) will be separately modeled for those patients who report a non-zero pain level. Risk factors will be evaluated, for **independent** association with the outcome variable, first for linearity and then for model fit using backward stepwise logistic regression (criterion  $P<0.05$ ). Model fit will be assessed by the Hosmer-Lemeshow test and validity of the fit models and predictive accuracy will be assessed using bootstrapping methods as well as the AUC 'c-index'. Analysis will also be performed on the raw NRS score (at 6 mo) using general linear models and mixed model regression as this may elucidate additional details about relationships among the factors and how they relate to pain at 6 mo. **Mediation** models will be evaluated based on techniques pioneered by Baron and Kenny, but with the modification of bootstrapping techniques to produce multiple mediator results with confidence intervals. Sobel method and  $R^2$  effect-size measures will be used to test and evaluate the mediation effects as well. Distributional assumptions and

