model fit will be evaluated for all models. **Moderating** effects will be tested using model building with predefined interactions for linear or logistic models.

Due to the extensive monitoring designed into our protocol we do not expect a large amount of missing data; however, the missing data that does arise will be handled using multivariate multiple imputation. Data not assumed to be missing at random, will be evaluated for systematic effects using sub-groups stratification. Statistical analyses will be performed using SAS version 9.1 (SAS Institute Inc, Cary, NC) or SPSS (SPSS for Windows, Rel. 16.0.1. 2007. Chicago: SPSS Inc.), with statistical significance determined with a Type I error threshold of  $\alpha = 0.05$ . For continuous outcome mediation analysis we will use a SAS macro (INDIRECT macro) and for dichotomous outcomes the SPSS macro version (INDIRECT macro) will be used, as the SAS macro version does not allow for dichotomous outcome variables.

**Primary endpoint:** The *primary endpoint* for the **Primary Aim** will be the incidence of PPP after TKR (similar to our power analysis), evaluated at 6 mo. For the **Secondary Aims**, the *primary endpoint* will be functional outcomes (ROM, WOMAC, SF-36,).

**Secondary endpoints:** The *secondary endpoint* for the Primary and Secondary Aims will examine additional parameterizations of PPP at 6 mo (NRS pain non-dichotomous, StEP neuropathic pain examination). Use of raw NRS pain scores may highlight functional (e.g. linear) relationships between pain and the predictive factors. Analysis will be performed as described for the primary outcome variable (incidence of PPP) but with the re-parameterized outcome variable and different model assumptions, depending on distributional properties. Each re-parameterization will be evaluated with respect to and compared with the primary outcome.

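### The general analysis section makes the primary outcome conditional (continuous 6-month NRS, with PPP as fallback), while the rest of the plan fixes PPP as primary

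*Combined protocol and SAP*

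**What the plan says.** The protocol and SAP are one document. Two outcomes are called primary in it.

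- **General statistical analysis, first statement.** The distribution of "the primary outcome, NRS pain scores at 6 mo, will be evaluated, transformed to normal and then modeled as a continuous variable". Should this fail, the dichotomous version "as defined for PPP, will be used".
- **General statistical analysis, next sentence.** "We expect that the primary outcome of PPP (dichotomous) will be modeled using a logistic regression". The reason given is that "the distribution of NRS pain scores from our preliminary survey data was strongly bi-modal (modes:0, 3". The section then plans a separate model of pain intensity in patients with non-zero pain, and general linear and mixed models of the raw 6-month NRS.
- **Power analysis and sample size calculation.** The one-year survey data "provides a conservatively estimate for the incidence of PPP at 6 mo, our primary outcome". The effect assumed is also for PPP: "we have an incidence of 15.5% at the mean and 30.3% at the mean plus one standard deviation".
- **Primary endpoint.** For the Primary Aim it "will be the incidence of PPP after TKR (similar to our power analysis), evaluated at 6 mo".
- **Secondary endpoints.** These are "additional parameterizations of PPP at 6 mo (NRS pain non-dichotomous, StEP neuropathic pain examination". The same paragraph refers back to PPP incidence as the primary outcome variable.
- **Detailed Analyses.** Under Independent Risk Factors, PPP is labelled the primary endpoint. The mediation hypothesis also has PPP incidence as its outcome.
- **Overall Strategy.** PPP is knee pain at six months in the operated knee, with other causes excluded and an NRS of at least 4.

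**The concern.** Continuous 6-month NRS is primary in one section and secondary in another. Both cannot hold. Read literally, the general analysis section sets an order of preference: try to normalise NRS and model it as continuous, and turn to PPP only on failure. It names no transformation, no normality test, no threshold and nobody to decide. Two analysts following it in good faith could declare different primary outcomes from the same data.

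The choice is more than one of labels:

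- **Definition.** PPP removes patients whose pain has another cause, such as infection or prosthetic failure. The raw NRS does not.
- **Effect measure.** One analysis gives an odds ratio for PPP. The other gives a slope on a transformed pain scale.
- **Sample size.** The sample size was derived for PPP only. The plan gives no power basis for a continuous NRS primary analysis.

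**Working it through.** The point concerns wording, so the main check sets the statements side by side.

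| Section | Outcome called primary | Condition | Status of continuous NRS |
|---|---|---|---|
| General statistical analysis, first statement | Continuous 6-month NRS | Unless it cannot be normalised and modelled | Primary |
| General statistical analysis, next sentence | Dichotomous PPP | Stated as an expectation | Not stated |
| Sample size | PPP incidence | None | Not mentioned |
| Primary endpoint | PPP incidence | None | Not mentioned |
| Secondary endpoints | PPP incidence | None | Secondary |
| Detailed Analyses | PPP | None | Not mentioned |

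Only the first row makes NRS primary. Every section outside General statistical analysis that names a primary outcome for the Primary Aim names PPP.

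**Which outcome the sample size supports.** The inputs, all from the sample size section, are 46 PPP cases among 259 patients, 15.5% PPP at the mean acute pain score, 30.3% at one SD above it, 90% power, alpha 0.05, squared multiple correlation 0.5 and 15% dropout.

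- Incidence: 46 / 259 = 17.8%, as stated and as repeated under Potential Difficulties and Limitations.
- Covariate step: 130 / (1 − 0.5) = 260, against the stated 259.
- Dropout step: 259 × 1.15 = 297.85, which gives the stated 298, rounded to 300.
- Starting value of 130: not reproduced. The odds ratio per SD is (0.303/0.697) / (0.155/0.845) = 2.37. With it, the Hsieh (1989) formula for logistic regression on one continuous predictor gives 122 patients one-sided and 152 two-sided. The plan does not state sidedness. This is a separate matter and nothing here depends on it.

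Every outcome input is an incidence of PPP. No mean, SD or slope for 6-month NRS appears.

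**Which branch the rule would probably take.** The preliminary data have modes at 0 and 3, and the plan reads them as two populations, one without pain. A one-to-one transformation moves a block of tied zeros to another value but cannot spread it out, so a large group of zeros cannot be made normal.

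To illustrate, assume 30%, 45% or 55% zeros, with non-zero scores rounded from a normal centred at 3 and limited to 1–10, and with the SD set so that 17.8% of all patients score 4 or more. The documents give none of these shares. Take 300 × 0.85 = 255 patients and 300 simulated datasets per setting. Shapiro-Wilk rejected normality in every dataset for raw, log(1+NRS), Box-Cox and rank-normal scores (largest p about 3e-12). Discreteness alone contributes to these rejections, and the plan names no test. Even so, on data like these the fallback applies and PPP is used.

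**The case against.** The strongest reply is that the plan already settles the matter. It has dedicated endpoint paragraphs that make PPP primary and continuous NRS secondary, and the sample size and detailed analyses agree. The general analysis section itself expects logistic regression of PPP and says why. On bimodal data the fallback leads to PPP under any sensible criterion, so the missing criterion would rarely matter.

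Most of this stands, and it is why the point is minor. It does not remove the contradiction. The sentence on PPP states an expectation, while the sentence before it states the rule. The expectation rests on a three-centre survey at one year, and the 6-month distribution in this single-site study could differ. No sentence says that the endpoint paragraphs override the rule.

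A reader might infer three stronger things, none of which the documents support:

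- **That type I error is inflated.** The stated trigger is the shape of the NRS distribution. That shape carries no information on which predictors are associated with pain, so either outcome would be tested at about its nominal level.
- **That the authors plan to choose the outcome by its results.** No section says so.
- **That the conclusions would often differ or power would be lost.** Putting a figure on this means assuming the share of zeros, a transformation that the plan does not name, and whether a predictor acts on the presence or the severity of pain. Distributions of the kind assumed would also trigger the PPP fallback. Such a figure would describe a branch that the rule would probably not take, so none is offered.

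**Conclusion.** Wrong as written, through internal contradiction; minor severity. The defect is confined to the General statistical analysis section, which lets the trial's own NRS distribution and an undefined judgement decide the primary outcome. The rest of the plan fixes PPP. Hypothesis 2 is unaffected because its outcome is already set as PPP incidence.

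The practical consequence is probably small. That rests on one assumption: that 6-month NRS scores will resemble the preliminary data, with a distinct group at zero. If they did not, and NRS were judged normal enough after transformation, the primary analysis would move to an outcome with a different definition and effect measure and no stated power. The documents do not allow the probability of that to be calculated.

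**What to change.** In General statistical analysis, replace the statement that makes continuous NRS primary, its fallback sentence, and the sentence expecting logistic regression. Suggested text:

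> The primary outcome is PPP (yes/no) at 6 months, as defined in the Overall Strategy. It will be analysed by logistic regression whatever the distribution of NRS scores. Continuous NRS at 6 months is a secondary outcome; its distribution will be examined and it will be transformed if needed. The preliminary survey scores had two modes, at 0 and 3.

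The sentence interpreting that distribution as two populations can follow unchanged. Keep the model of non-zero pain and the general linear and mixed models of raw NRS, each labelled secondary, in line with the Secondary endpoints paragraph. The mediation text needs no change.

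The cost is three sentences replaced and two analyses labelled, all in one section. No data collection or analysis is added, and the planned 300 stays because it was computed for PPP.

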**Covariates:** Preoperative covariates included are as follows: age, weight/BMI, OA severity and ASA status. Perioperative covariates include: postoperative analgesic consumption and duration of surgery. Complications after TKR will be recorded and included as a summed incidence. Patient questionnaires of drug use in the first three wks postoperatively will be converted to daily morphine equivalents and included as a covariate in the predictive models. Although the protocol stipulates uniformity in medication use during the acute postoperative period, once the patient leaves the hospital, their analgesic use over the next 6 mo cannot be rigidly controlled. To reduce variation we will prescribe analgesics as needed (per protocol above mentioned) and will remain in contact with the patients to record additional medication.

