- 1) **Neurophysiologic:** Expected Result: (Hypothesis 2): Area of secondary hyperalgesia post-TKR will mediate links between preoperative pain sensitivity and PPP incidence: (preop thermal sensitivity score affects area of mechanical secondary hyperalgesia which in turn leads to increased PPP incidence) will fit the data significantly better than the independently predictive model (preop thermal sensitivity score will directly affect PPP incidence).
- 2) **Psychosocial:** Expected result: (Hypothesis 2): Area of secondary hyperalgesia will mediate links between pain anxiety/catastrophizing and PPP (ex. pain anxiety PASS score → area of secondary hyperalgesia → PPP incidence).

**Secondary Aims:** Test for risk moderators.

C. **Moderation Models:** Test for risk moderators:

*Hypotheses 4 postulates that patient age will moderate the relationship between risk factors and PPP development. We expect the predictive relationship between preop pain sensitivity and PPP incidence to be stronger (enhanced) among younger as opposed to older patients*

- 1) **Demographics:** Expected Result: The effect of preop pain sensitivity on PPP will be moderated by age (ex. direct effect is: ↑ preop thermal NRS score → ↑PPP incidence; but moderating effect is: ↑ preop thermal NRS score x ↓age → ↑↑PPP incidence)

**Omnibus Model:** To create a more complete description of the factors, mechanisms and interrelationships involved in development of PPP, several omnibus models will be created and evaluated. Knowledge gained from each of the individual aims will be utilized to create this model, using principal component and factor analysis for variable reduction and predictive modeling with particular focus on mediation between the domains and the aims.

**The prediction equation:** To highlight the risk factors for PPP, including importance (weighting) and interactions, in not only the preoperative phase but in the postsurgical phase, a prediction equation will be described. The use of the prediction equation can then be validated and fine tuned in later studies. A simple example formula for the prediction equation:

$$Pr_i = \frac{1}{1 + \exp(a + \beta_1 Age_i + \beta_2 preOpPainSens_i + \beta_3 SecHyperal_i + \beta_4 postOpNRS_i + \beta_5 TraitAnxiety_i + \beta_6 Catastrophizing_i)}$$

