#### Potential Difficulties and Limitations

1. We have no way of directly assessing minor nerve damage following TKR.
2. Patient may decide to undergo another elective joint replacement procedure during the 6-mo postop period
3. Although power analysis is based on 17.8% PPP incidence, TKR procedures may vary over the 3-yr duration of study. However our power estimates are conservative and our multivariate analyses are robust and powerful.
4. 6 mo assessment of PPP can be complicated by opioid use in some patients. However, this factor is considered as a covariate in the analysis.

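### The plan does not say that backward selection is repeated inside the bootstrap and plans no shrinkage, so with about 45 PPP cases the c-index may be overstated and predicted risks will usually be too extreme

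*Combined protocol and SAP*

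**What the plan says.** The General statistical analysis section sets an order of work. Risk factors are checked for linearity and then reduced by backward stepwise logistic regression at P<0.05. Fit is examined with the Hosmer-Lemeshow test, and "validity of the fit models and predictive accuracy will be assessed using bootstrapping methods as well as the AUC 'c-index". What happens inside each resample is not described. Missing data are to be multiply imputed, with no statement of how imputation and bootstrap are combined.

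Under The prediction equation, the plan says that, to highlight the risk factors, "including importance (weighting) and interactions, in not only the preoperative phase but in the postsurgical phase, a prediction equation will be described". The example formula is an ordinary logistic model in six terms: age, preoperative pain sensitivity, secondary hyperalgesia, postoperative NRS, trait anxiety and catastrophizing. Validation and fine-tuning are left to later studies. Shrinkage, penalisation, optimism correction and calibration slope are not mentioned.

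The Covariates section begins "Preoperative covariates included are as follows: age, weight/BMI, OA severity and ASA status". It adds postoperative analgesic consumption, duration of surgery, a complication count and opioid use in the first three weeks. It does not say whether these compete in the backward selection, are forced into the model, or stay out of the prediction equation.

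**The concern.** When the data choose the terms, the choice itself produces optimism. A bootstrap that refits only the chosen terms misses that part. It removes too little from the c-index and can suggest that the coefficients need no shrinkage. A bootstrap that repeats the choice in each resample does measure it. The plan's wording allows either.

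Shrinkage is a separate matter. Maximum-likelihood coefficients from few events per term tend to be too large in new patients, whichever bootstrap is used, so high predicted risks come out too high and low ones too low. The Detailed Analyses section links Hypothesis 1 to clinical prediction models, and Future Directions foresees enriched trials in patients at high risk. Exaggerated risks at the upper end would matter most for the second use. Validation in later studies would not correct the c-index and weights that this study reports.

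**Working it through.** **Inputs from the plan.** The power section reports, among 259 survey patients, that "46 (17.8%) were identified with PPP at one year after surgery": 46/259 = 17.8%, which reproduces. For the total it says "With a 15% dropout rate this values climbs to 298 (round to 300": 259 x 1.15 = 298, which also reproduces. Nothing below depends on the earlier steps of the sample-size calculation.

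**Expected cases.** 300 x 0.85 = 255 completers, and 255 x 0.178 = 45.4 cases. At the 13% to 20% incidence quoted in the Significance section this is 33 to 51. If all 300 are analysed after imputation it is 53.

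**Terms.** The Primary Aims list five risk factors: thermal sensitivity, anxiety, catastrophizing, hyperalgesia area and postoperative pain. Adding age gives the six of the example equation. Adding the other seven covariates (weight/BMI, OA severity, ASA status, analgesic consumption, duration of surgery, complications, three-week opioid use) and the age-by-sensitivity interaction gives 6 + 7 + 1 = 14.

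**Cases per term.** 45.4/6 = 7.6 and 45.4/14 = 3.2.

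**Effect sizes for simulation.** The plan's figures imply two values for acute pain. The odds ratio of 1.24 per point over an SD of 2.9 gives 1.24^2.9 = 1.87 per SD. The statement that "we have an incidence of 15.5% at the mean and 30.3% at the mean plus one standard deviation" gives (0.303/0.697)/(0.155/0.845) = 2.37 per SD. Both were tried. The effects of the other predictors and the pairwise correlation of 0.2 are assumptions.

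**Simulation, 14 candidates.** n = 255, 17.8% incidence, backward elimination at P<0.05, 40 bootstraps per data set, performance checked in 20,000 new patients. Two of the patterns (means):

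| | Pain OR 1.87 per SD, four others at log-OR 0.2 (200 data sets) | Pain OR 2.37 per SD, no other effect (100 data sets) |
|---|---|---|
| Apparent c-index | 0.744 | 0.733 |
| Bootstrap of the selected model only | 0.733 | 0.726 |
| Bootstrap repeating the selection | 0.684 | 0.677 |
| c-index in new patients | 0.689 | 0.704 |
| Calibration slope in new patients | 0.752 | 0.888 |
| Slope estimated by selected-model bootstrap | 1.062 | 1.011 |
| Slope estimated by full bootstrap | 0.728 | 0.745 |

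The selected-model bootstrap overstates the c-index by 0.733 - 0.689 = 0.044 in the first pattern and by 0.726 - 0.704 = 0.022 in the second. In the first it was too high in about 85% of data sets, and the slope in new patients was below 1 in 89%.

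**Six terms.** With only the six equation terms as candidates, the overstatement was about 0.01 to 0.03. When the six were fitted with no selection, the mean slope was 0.70, 0.81 and 0.85 in three effect patterns, so over-extreme risks do not depend on counting 14 terms.

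**What the slope means for a patient.** With m = ln(0.178/0.822) = -1.53 and slope s, a predicted 50% corresponds to expit(m(1 - s)). For s = 0.7: expit(-0.459) = 39%. For s = 0.9: expit(-0.153) = 46%.

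**The case against.** The strongest reply is that the plan is silent rather than wrong. Bootstrapping predictive accuracy is compatible with repeating the whole procedure. A reader might infer that the plan resamples only the final model and that the c-index is certain to be inflated. The text suggests this, because the thing to be validated is the fitted model, but does not establish it. That part of the point is therefore conditional.

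A reader might also take 14 candidates as the plan's number. It is a count of listed terms. The plan applies selection to risk factors, says that covariates are included, and tests interactions separately. The reading changes the result. If the eight covariates are forced in and only five risk factors are selected, most of the optimism comes from estimating forced terms. Resampling the fitted model then already lowers the c-index by 0.05 to 0.07, and repeating the selection still leaves it 0.01 to 0.03 too high. Calibration is worse in that case (slope 0.49 to 0.62), so shrinkage matters more and the resampling detail less.

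Nor is the full bootstrap exact. In the second pattern above it was too low, by 0.704 - 0.677 = 0.027, and its slope of 0.745 against 0.888 would shrink too much.

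Three further inferences go too far:
- The Hosmer-Lemeshow test is assigned to model fit and validity to the bootstrap, so it cannot be said that calibration rests on that test alone.
- The remark in Potential Difficulties and Limitations that "our power estimates are conservative and our multivariate analyses are robust and powerful" concerns power when procedures vary. It makes no claim about prediction accuracy.
- The risk/benefit sentence under Implications for Clinical Practice is about the relative risk of modifiable factors. It does not mention the equation.

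The plan also calls its formula a simple example and expects later refinement. That lowers the stakes, but the c-index and weights would still be reported from this study.

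**Conclusion.** The point holds in a limited form. The plan leaves open whether selection is repeated in the bootstrap and provides for no shrinkage, while its own figures imply about 45 cases for 6 to about 14 terms. If only the selected model is resampled, the c-index would be about 0.01 to 0.05 too high. Whichever bootstrap is used, the unshrunk equation would usually have a slope of about 0.7 to 0.9, and lower if all covariates are forced in. The exception was selection among six candidates with a single true effect, where one simulation did not find a mean slope below 1.

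A reader might infer a slope near 0.66, which would turn a predicted 50% into about 37%. For selection among 14 candidates that is the low end: other runs gave 0.71 to 0.89 in new patients. All these sizes rest on assumed effects and correlations. The direction is well supported, the exact amount is not. This is a cheap improvement to the analysis plan rather than a demonstrated error in it.

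**What to change.** In General statistical analysis:
- state the candidate set, and for each item under Covariates say whether it is selected, forced in or left out of the prediction equation;
- repeat every data-driven step used to build the equation (imputation, linearity checks, backward selection) in each bootstrap sample;
- report the optimism-corrected c-index and calibration slope alongside the Hosmer-Lemeshow test.

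Under The prediction equation, multiply the coefficients by the bootstrap calibration slope and re-estimate the intercept, or fit the equation by penalised logistic regression. The plan does not say that the principal component and factor analysis of the Omnibus Model feeds the equation. If it does, it belongs inside the resampling as well.

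The cost is wording and some programming, with no added patients or visits. The reported c-index will be less favourable and the predicted risks less extreme.

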## Approach

**Overall Strategy:** The primary aim of this application is to investigate relationships of risk factors to the development of PPP at 6 mo following TKR, through independently predictive and mediated models. These risk factors are preoperative thermal pain sensitivity, pain anxiety and catastrophizing; postoperative area of secondary mechanical hyperalgesia or hypoalgesia (numbness) and pain intensity. **PPP** for this study will be defined as "**pain in the operated knee at six months after TKR, with other causes of pain excluded and reported intensity on 0-10 NRS scale of  $\geq 4$ .**" The study will also evaluate the relationship of PPP incidence with the severity of functional impairment. This is a single-site prospective clinical investigation of 300 consented OA patients undergoing primary, unilateral TKR. Although we realize the importance of genetic susceptibility on the development of PPP, the complexity of determining the multiple genes that may contribute to this condition is beyond the scope of this proposal. However, prior to surgery we will obtain a blood sample (8.5 mL) from all patients, process it for DNA analysis, and store at -80° C for future studies by [name], NINR (letter of support) to screen for genetic predictors of PPP, such as COMT and GCH1. We will also obtain three blood samples (5ml each) for RNA analysis. In a previous IRB approved study, we also obtained blood samples for RNA analysis prior to hip replacement surgery and 24 hours afterward and found that IL18R1 was up-regulated while IL-8RB was down-regulated and may be related to the normal acute post

operative inflammation. However, we now need to examine the changes in cytokine gene expression in the TKR patients. All of the blood samples will be sent for analysis to [name] laboratory. The patients' genetic information will stay confidential, and will be identified by a study number, and not a name. This information will not be disclosed to any other third party. Personal data will be stored at Rush University Medical Center. The samples sent to [name] laboratory will be appropriately coded so that the patient's name does not appear on the samples. Data will be kept for 1 year from the time the last patient is enrolled in the study.

Study Calendar	Preop	Post-Incision				Post-operative			
		24h	36h	48h	72h	3 wk	6 wk	3 mo	6 mo
General Physical Examination	X					X	X	X	X

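### The only step planned for 6-month outcomes that are not missing at random is sub-group stratification, which cannot detect or correct dropout that depends on the unseen pain score

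*Combined protocol and SAP*

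**What the plan says.** The paragraph on missing data follows the General statistical analysis text. It begins from the expectation, based on close monitoring, that "we do not expect a large amount of missing data". It then says that "the missing data that does arise will be handled using multivariate multiple imputation", without listing the variables in the imputation model. The last element is the sentence "Data not assumed to be missing at random, will be evaluated for systematic effects using sub-groups stratification". No strata, estimator, decision rule or consequence is attached to it. Neither the protocol nor the SAP mentions a delta adjustment, a pattern-mixture or selection model, a tipping point, or best and worst-case bounds.

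The power section builds in a loss allowance: "With a 15% dropout rate this values climbs to 298 (round to 300". It takes its incidence from the sponsor's survey, in which "259 TKR patients fell within criteria, of which 46 (17.8%) were identified with PPP at one year after surgery". The primary endpoint is incidence of PPP at 6 months. The Overall Strategy paragraph defines PPP as an NRS of at least 4 in the operated knee with other causes of pain excluded.

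**The concern.** A patient may miss the 6-month visit because the knee no longer hurts, or because it still hurts and care was sought elsewhere. In both cases the chance of being missing depends on the value that is missing. Comparing sub-groups can show that dropout differs by age or by earlier pain, but an imputation model can already use that information. It cannot show whether, within a stratum, the patients who left had more or less pain at 6 months than those who stayed. Nor does an evaluation by sub-group change any estimate.

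The sponsor therefore recognises that non-random missingness may occur but names a tool that would return a reassuring answer whether or not it had. The quantities at stake are the incidence itself, the absolute risks from the prediction equation, and the planned linear models of raw 6-month NRS.

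**Working it through.** **Inputs.** From the power section: 259 patients before dropout, 15% dropout, 298 rounded to 300, and PPP in 46 of 259. The range of odds ratios for dropouts against completers (0.5 to 3) is an assumption; the documents give none.

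**The plan's own figures.** 46/259 = 17.8%, as stated. 259 × 1.15 = 297.85, which gives the stated 298. (Dividing instead, 259/0.85 = 304.7, would give 305; that is a separate and small matter.)

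**Patients without the outcome.** 0.15 × 300 = 45, leaving 255 completers. Expected PPP cases among completers: 255 × 0.178 = 45.4.

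**Incidence when dropouts differ.** Completers' odds of PPP = 0.178/0.822 = 0.2165. With odds ratio k for dropouts, p = 0.2165k/(1 + 0.2165k), and overall incidence = (45.39 + 45p)/300.

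| Assumption for the 45 dropouts | p | Overall incidence |
|---|---|---|
| none has PPP | 0 | 15.1% |
| k = 0.5 | 0.098 | 16.6% |
| k = 1 (same as completers) | 0.178 | 17.8% |
| k = 2 | 0.302 | 19.7% |
| k = 3 | 0.394 | 21.0% |
| all have PPP | 1 | 30.1% |

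**What stratification would show.** A large simulated cohort had 17.8% incidence, an odds ratio of about 2.38 per SD of one risk factor, 15% missing overall, and PPP doubling the odds of being missing. Splitting it at the median of the risk factor gives missing rates of 15.9% and 14.1%. In 300 patients that is about 24 against 21 of 150 in each half, a gap too small to notice. Even if noticed, it would look the same as missingness that depends on the risk factor alone.

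**What happens to odds ratios.** For completers, logit P(PPP | x) equals the true logit plus ln[P(observed | PPP, x)/P(observed | no PPP, x)]. If missingness depends on PPP alone, the added term is a constant, so the intercept moves and the slope does not. In the same simulation, missing rates of 23.2% with PPP and 13.2% without give ln(0.768/0.868) = −0.12, and the fitted intercept fell by 0.12. Results among completers:

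| Missingness (assumed scenarios) | Incidence | Odds ratio per SD |
|---|---|---|
| none | 17.8% | 2.38 |
| PPP doubles the odds of being missing | 16.1% | 2.38 |
| PPP triples the odds of being missing | 14.9% | 2.38 |
| depends jointly on PPP and the risk factor | 15.4% to 18.5% | 1.91 to 2.75 |

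**The case against.** The strongest reply is that multiple imputation is the main method and that stratification is only said to evaluate. That is correct: it would be wrong to infer from the sentence that the plan handles missing outcomes by stratification. But imputation does not test its own assumption, and stratification is the only step offered for when that assumption fails. The term sub-groups is undefined and could mean dropout patterns. Even so, comparing patterns on observed data says nothing about the unseen score.

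Second, contact is frequent. NRS is taken at the 3-week, 6-week and 3-month visits and every 20 to 30 days from 3 to 6 months, so a patient who misses the last visit may have a score from the month before. This would make missing at random more plausible if those scores entered the imputation model. The plan does not say that they do.

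Third, the assumed incidence range is modest. The sampling error of 17.8% in 255 patients is √(0.178 × 0.822/255) = 2.4 points, a 95% interval of about 13.1% to 22.5%, which contains 16.6% to 21.0%. That stands as a comment on size. However, a shift from dropout is systematic, and the reported interval does not include it.

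Three stronger readings are tempting but not supported:

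- **That 15% dropout contradicts the expectation of little missing data.** A planning margin and an expectation can both hold; there is tension, not contradiction.
- **That dropouts matching PPP cases in number (45 and 45) is meaningful in itself.** The match depends on the denominator: 300 − 259 = 41 or 298 − 259 = 39 against 46 cases, or 45 against 53 in all 300. It conveys scale only.
- **That the Hypothesis 1 odds ratios must be biased.** The simulation shows that they are not when missingness depends on PPP alone.

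**Conclusion.** The point holds. The plan names the possibility of non-random missingness and assigns it a method that can neither detect nor correct it, and no other sensitivity analysis appears. At 15% dropout and 17.8% PPP among completers, overall incidence runs from 16.6% to 21.0% under the assumed odds ratios of 0.5 to 3, with limits of 15.1% and 30.1%. The upper limit requires every dropout to have PPP and is a bound, not a forecast.

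Incidence, the prediction-equation intercept and linear models of raw NRS are exposed to any dropout related to 6-month pain. Logistic odds ratios, the main currency of Hypothesis 1, are exposed only if missingness depends jointly on PPP and the risk factor; the values 1.91 to 2.75 against 2.38 illustrate assumed scenarios of that kind. The base method is standard, so this is a weakness in the robustness analysis and does not invalidate the primary analysis.

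**What to change.** 1. Keep multiple imputation as the base analysis. State the imputation model and include in it the serial NRS already collected: the 3-week, 6-week and 3-month visits and the contacts between 3 and 6 months.
2. Replace the stratification sentence with a delta-adjusted sensitivity analysis that shifts the log-odds of imputed PPP over a stated range, for example odds ratios of 0.5 to 3, labelled as an assumption.
3. Impute PPP status directly; do not re-derive it from shifted NRS. The sponsor's survey scores had modes at 0 and 3, so adding one point would move every imputed 3 across the cut-off of 4, and the result would reflect the cut-off. A shifted score also cannot supply the exclusion of other causes that the definition requires.
4. Across the range, report incidence with the best and worst-case bounds, and the Hypothesis 1 odds ratios from one fixed, pre-specified multivariable model. Under the planned backward selection the set of predictors could change with each shift, so the point at which a conclusion changes would be ambiguous.
5. Also let the shift vary with the risk factor. A constant shift moves mainly the intercept and would barely test the odds ratios.

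The cost is SAP wording and a few extra imputation runs, with no new data. The downside is slightly less favourable stated certainty in the report.
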